10.1 Early Stopping

In the event that the study is stopped early due to efficacy concerns based on results of the parent study, no inferential efficacy analysis will be carried out. No outputs for the efficacy endpoints will be presented.

The list of outputs produced in the case the study is stopped early are provided in 16Appendix 1: List of Tables, Figures and Listings.

10.2 Secondary Efficacy Analysis

10.2.1 Responder Analysis

10.2.1.1 Estimands

The key secondary response endpoints will be evaluated at all scheduled visits and are as follows:

- EASI-50, EASI-75, EASI-90
- IGA of 0 or 1 with a ≥ 2 -point improvement from baseline
- IGA of 0 or 1
- BSA-50, BSA-75
- SCORAD-35, SCORAD-50, SCORAD-75
- Improvement of ≥ 4 points in POEM score from baseline*

The other secondary endpoints are:

- IGA of 0
- BSA $\leq 3\%$
- Improvement of ≥ 4 points in DLQI from baseline*
- Improvement of ≥ 2 points in PP-NRS score from baseline*
- Improvement of ≥ 4 points in PP-NRS score from baseline*
- Improvement of ≥ 2 points in SD-NRS score from baseline*

* Of those with a relevant score of $\geq 2/4$ at baseline

The population summary measure of interest for all response estimands will be the percentage of participants with the relevant response at each visit.

Intercurrent events for response endpoints will be accounted for in the following manner:

Table 2: Intercurrent Event Strategies of the Secondary Response Endpoints

Estimand	DPS	Use of TCS/TCI rescue medications within 4 weeks or type 1 prohibited meds from 207, use at any time of other prohibited medications for atopic dermatitis, discontinuation of treatment for treatment failure related reasons*	Discontinuation of treatment for reasons not related to treatment-failure**, non-compliance with study drug, any other deviations from the protocol
Response Estimand 1	DPS4b	Composite strategy Replace with 'non-response' all data collected 1) within 4 weeks after the use of TCS/TCI rescue medications or type 1 prohibited meds from 207 2) at any time after the use of other prohibited medications for atopic dermatitis 3) at scheduled visits after treatment discontinuation for treatment-related reasons*	Treatment policy strategy All data is used regardless of the intercurrent event
Supplementary Response Estimand 1	DPS4	Treatment policy strategy Include all data collected regardless of use of TCS/TCI rescue medications or other prohibited medications for atopic dermatitis or treatment discontinuation	Treatment policy strategy (as per response estimand 1)
Supplementary Response Estimand 2	DPS4a	If rescue or prohibited medications used: While on treatment strategy Exclude all data collected within 4 weeks after the use of TCS/TCI rescue medication or at any time after the use of other prohibited medications for atopic dermatitis If treatment discontinuation: Treatment policy strategy All data is used regardless of the treatment discontinuation	Treatment policy strategy (as per response estimand 1)

* related AEs, lack of efficacy, requirement for alternate psoriasis therapy

** participants will be withdrawn from the study following discontinuation of treatment and as such it is expected that data collected at the scheduled visits will only include participants who are on treatment (or very recently discontinued) with the exception of those visits specifically scheduled to occur 4 and 12 weeks after last dose.

All response secondary endpoints will be analysed with a response estimand 1 (DPS4b). Key secondary endpoints will be also analysed with supplementary response estimands 1 and 2 (DPS4 and DPS4a).

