11.6. Handling of Dropouts or Missing Data

Unless otherwise specified as part of the intercurrent event strategy, missing data will not be imputed.

Otherwise, missing data will not be imputed.

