7.1.2.4 Data Point Set 4 (DPS4)

DPS4 consists of all observed data collected at a scheduled visits in this study or the parent study for participants who enter this study.

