7.1.2.5 Data Point Set 4a (DPS4a)

DPS4a is a subset of DPS4, excluding any data collected within 4 weeks after the use of permitted rescue medications for atopic dermatitis or at any time after the use of prohibited medications for atopic dermatitis.

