7.1.2.6 Data Point Set 4b (DPS4b)

DPS4b is a subset of DPS4 for responder endpoints only, where data collected within 4 weeks after the use of permitted rescue medications for atopic dermatitis, at any time after the use of prohibited medications for atopic dermatitis, or at scheduled endpoints after withdrawal from treatment due to treatment-failure related reasons (related AEs, lack of efficacy, requirement for alternate psoriasis therapy) will be replaced by 'non-responder'.

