7.3 Missing Data

Unless otherwise specified as part of the intercurrent event strategy, missing data will not be imputed. Imputation of missing efficacy data due to intercurrent events will be performed in DPS4a and DPS4b as described in [Section 7.1.2](#).

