10.3 Exploratory Efficacy Analysis

10.3.1 Time to Event Analysis

10.3.1.1 Estimands

The exploratory time to event endpoints are:

- Time to first achievement of EASI-50
- Time to first achievement of sustained EASI-50 (See section 5.3.3.1)

The population summary measure of interest will be the cumulative percentage of participants achieving response at each scheduled visit.

Intercurrent events for the exploratory time to event endpoints will be accounted for in the following manner:

Table 5: Intercurrent Event Strategies for Time to Event Estimand 1

Use of TCS/TCI rescue medications within 4 weeks or type 1 prohibited meds from 207, use at any time of other prohibited medications for atopic dermatitis	Treatment discontinuation, non-compliance with treatment, other deviations from the protocol
Composite strategy Participants will be considered as ‘non-responders’ 1) within 4 weeks after the use of TCS/TCI rescue medications or type 1 prohibited meds from 207 2) at any time after the use of other prohibited medications for atopic dermatitis	Treatment policy strategy: Data will be used as collected

For all exploratory time to event endpoints data point set DPS4b will be used.

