10.3.3 Responder Analysis

10.3.3.1 Estimands

The exploratory response endpoints are:

- Achievement of 50% reduction in each of the four region scores of the EASI
- Change in response states from Day -1 to weeks 8, 16, 24 and 36. Response states will be defined using the EASI score percentage change from baseline with categories for: $\geq 25\%$ increase, no change (<25% increase to <25% decrease), 25% to <50% decrease, 50% to <75% decrease, 75% to <90% decrease, $\geq 90\%$ decrease

Achievement of 50% reduction in each of the four region scores of the EASI

The population summary measure of interest will be the percentage of participants achieving response at each visit.

Change in response states from Day -1 to weeks 8, 16, 24 and 36

The population summary measure of interest will be the percentage of participants with each change in response state.

Intercurrent events will be accounted for in the following manner:

Table 7: Intercurrent Event Strategies of the 50% reduction of EASI in body regions

Use of TCS/TCI rescue medications within 4 weeks or type 1 prohibited meds from 207, use at any time of other prohibited medications for atopic dermatitis	Treatment discontinuation, non-compliance with treatment, other deviations from the protocol
Composite strategy Participants will be considered as ‘non-responders’ 1) within 4 weeks after the use of TCS/TCI rescue medications or type 1 prohibited meds from 207 2) at any time after the use of other prohibited medications for atopic dermatitis	Treatment policy strategy: Data will be used as collected

Data point set DPS4b will be used for exploratory response endpoints.

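### Does the SAP's promise to impute missing responder data, with no rule for an absent visit, leave treatment failures out of the denominators?

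*SAP*

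**What the plan says.** SAP section 7.3 first rules out imputation except where an intercurrent-event strategy calls for it. It then adds: "Imputation of missing efficacy data due to intercurrent events will be performed in DPS4a and DPS4b", and refers the reader to section 7.1.2 for the method.

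The definitions there are as follows.

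- Section 7.1.2.4: "DPS4 consists of all observed data collected at a scheduled visits in this study or the parent study".
- Section 7.1.2.5: "DPS4a is a subset of DPS4, excluding any data collected within 4 weeks after the use of permitted rescue medications for atopic dermatitis". Data after a prohibited medication are also removed.
- Section 7.1.2.6: DPS4b is a subset of DPS4 in which collected data become non-response in three situations. The third is "at scheduled endpoints after withdrawal from treatment due to treatment-failure related reasons".

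Table 2 in section 10.2.1.1 repeats the three situations for Response Estimand 1, the main estimand for every secondary response endpoint. Item 3 covers data collected "at scheduled visits after treatment discontinuation for treatment-related reasons".

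DPS4b also serves the exploratory analyses. Section 10.3.1.1 states: "For all exploratory time to event endpoints data point set DPS4b will be used". Section 10.3.3.1 states: "Data point set DPS4b will be used for exploratory response endpoints". Tables 5 and 7 in those sections handle treatment discontinuation by treatment policy.

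Protocol section 11.6 closes with: "Otherwise, missing data will not be imputed".

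**The concern.** Section 7.3 promises imputation and points to a section that contains none. A data set that only excludes records cannot impute, and a subset of observed data cannot hold a value for a visit that did not take place.

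This would matter for item 3 of the composite strategy. Participants who fail treatment are withdrawn, so they have almost no later scheduled visits whose data could be replaced. If they simply disappear, the composite estimand becomes a response rate among those still attending, which is too high. Two programmers could follow the same SAP and report different percentages.

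Three smaller points seemed to add to this:

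- Tables 5 and 7 use DPS4b but do not carry its treatment-failure limb.
- Item 3 of Table 2 speaks of treatment-related reasons, where its column header speaks of treatment failure.
- The listed reasons name psoriasis, which is not this trial's indication.

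**Working it through.** **1. Path of a participant withdrawn for treatment failure**

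| Step | Source |
|---|---|
| Stops study drug and is withdrawn from the study | Protocol 5.4 |
| Has an Early Termination visit, then a telephone call for safety | Protocol 7.4 |
| The Early Termination visit is kept out of summary and analysis tables, except as a baseline value or for worst-case safety | SAP 7.7 |
| Percentages use participants with non-missing data | SAP 8 |
| Scheduled-visit data are expected essentially only from participants on, or just off, treatment | SAP Table 2, second footnote |

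Read literally, the participant leaves the 208 denominators. The 207 visits are not affected, because withdrawal in 208 comes later.

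**2. Size under the literal reading**

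Let R be the responders at a visit, N the participants with data, and F the withdrawn failures without data.

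- Literal percentage: R/N.
- Percentage with failures as non-responders: R/(N + F).
- Ratio: (N + F)/N = 1/(1 − f), with f = F/(N + F).
- Check: N = 90 and F = 10 give f = 10% and 100/90 = 1.11.

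The documents give neither f nor a response rate, so both are assumed here. The last two columns are the literal percentage times (1 − f).

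| Assumed f | Factor 1/(1 − f) | Literal 20% becomes | Literal 40% becomes |
|---|---|---|---|
| 5% | 1/0.95 = 1.05 | 19.0% | 38.0% |
| 10% | 1/0.90 = 1.11 | 18.0% | 36.0% |
| 20% | 1/0.80 = 1.25 | 16.0% | 32.0% |
| 30% | 1/0.70 = 1.43 | 14.0% | 28.0% |

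**3. Which reading the text supports**

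The third limb of DPS4b is separate from the rescue and prohibited-medication limbs. Because treatment failures leave the study, it has almost no content unless it reaches visits they did not attend. Section 7.3 says that data missing because of an intercurrent event are to be filled in, and the only value DPS4b supplies is non-response. Together they lead an analyst to count these participants as non-responders.

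**4. Which outputs depend on it**

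Tables on DPS4b in SAP Appendix 1 (16.2.1):

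- Under Table 2: EASI 3 + vIGA 3 + BSA 3 + SCORAD 3 + DLQI 1 + PP-NRS 2 + SD-NRS 1 + POEM 1 = 17.
- Under Tables 5 and 7: time to event 2 + regional 50% reduction 1 + response states 1 = 4.
- Total: 17 + 4 = 21.

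Section 16.2.2 lists 14 figures on DPS4b, so 21 + 14 = 35 outputs. All 35 have No in the Early Stop column.

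The outputs marked Yes cover disposition, region and site, demography, exposure, adverse-event tables on DPS1, and four listings. None uses DPS4a or DPS4b. SAP 10.1, SAP 16.2 and the last rows of Table 9 agree: the study was terminated early and efficacy outputs are dropped. The number of outputs still to be produced that depend on the rule is 0.

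**5. Tables 5 and 7**

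For time to first EASI-50, an absent visit and a non-response visit both contribute no event, and SAP 10.3.1.2 divides by participants at risk. The conflict therefore has little practical content there. For the two exploratory responder tables the denominator question is the same as in step 2. Neither table is produced.

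**The case for a change.** The best argument for changing the text is that the SAP still carries the complete efficacy specification, with DPS4b as the main data set for every secondary response endpoint. The words describe replacing collected data within observed data, and good intent does not remove that. A correction would cost only wording. In the full package, 35 outputs would rest on the rule and the point would not be small. That much stands: the gap is real, and it would have to be closed before any responder analysis were run.

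Other parts do not stand.

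- **A departure from the protocol.** It can be argued that the imputation sentence in 7.3 is an unlisted change from Protocol 11.6. But 11.6 opens by excepting whatever the intercurrent-event strategy specifies, and SAP 7.3 opens the same way. Replacement by non-response is already in Protocol 11.2.2 and 11.3.2. No entry in Table 9 is missing.
- **The label in item 3.** It carries the same asterisk as the column header, and the footnote defines the reasons. No analyst would be misled.
- **The psoriasis wording.** This is a carry-over from another indication and is clerical.
- **The size.** The factors in step 2 follow from assumed values of f and from a reading that the SAP as a whole does not favour.

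**Conclusion.** No change to the plan follows, because there is nothing to gain. SAP 7.3 is loosely drafted: it names DPS4a, which imputes nothing, and it relies on a DPS4b definition worded for collected data only. The evident intent is that treatment failures count as non-responders, and an analyst reading 7.3 with 7.1.2.6 would arrive there.

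Under the plan in force, 0 of 35 DPS4b outputs are produced. All analyses are descriptive, so no test or error rate is touched. The safety package does not use these data sets.

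This conclusion rests on the efficacy outputs staying cancelled. If a responder analysis were reinstated, the literal reading could overstate a Table 2 percentage by a factor of 1.05 to 1.43 over the assumed range of f. The handling of later scheduled 208 visits that were not attended, and whether the treatment-failure limb applies to Tables 5 and 7, would then have to be stated first.

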10.2.1.2 Analytical Approach

Summary tabulations of frequency and percentage of participants within each category will be presented at each scheduled visit that the variable is recorded. The following visits should be presented unless otherwise stated: Baseline, 207 Week 4, 8, 12, 16 (labelled as “207 / Week X”) and 208 week 4, 8, 12, 16, 24, 36, 40 (labelled as “208 / Week X”).

Figures for the proportion of participants achieving response over time for each of the criteria will be created for the same scheduled visits as summaries.

10.2.2 Continuous Variables Analysis

10.2.2.1 Estimands

The secondary continuous endpoints are as follows:

- Change and percentage change from baseline in EASI score
- Change and percentage change from baseline in IGA*BSA
- Change and percentage change from baseline in BSA
- Change and percentage change from baseline in SCORAD score
- Change and percentage change from baseline in DLQI score
- Change and percentage change from baseline in POEM score
- Change from baseline in PP-NRS*
- Change from baseline in SD-NRS*

* The score at each visit is calculated as the mean daily score for the 7 days prior to and including the visit date. At least 4 daily scores must be available for the score at the relevant visit to be considered evaluable.

The population summary measure of interest will be the mean at each scheduled visit.

Intercurrent events for continuous estimand 1 will be accounted for in the following manner:

Table 3: Intercurrent Event Strategies of Continuous Estimand 1

Use of TCS/TCI rescue medications within 4 weeks or type 1 prohibited meds from 207, use at any time of other prohibited medications for atopic dermatitis	Discontinuation of treatment for any reason*, non-compliance with study drug, any other deviations from protocol
While on treatment strategy Exclude all data collected 1) within 4 weeks after the use of TCS/TCI rescue medications or type 1 prohibited meds from 207 2) at any time after the use of other prohibited medications for atopic dermatitis	Treatment policy strategy All data is used regardless of the intercurrent event

* participants will be withdrawn from the study following discontinuation of treatment and as such it is expected that data collected at the scheduled visits will only include participants who are on treatment (or very recently discontinued) with the exception of those visits specifically scheduled to occur 4 and 12 weeks after last dose.

Note, for PP-NRS and SD-NRS intercurrent event strategy should be applied for daily scores before the weekly scores are calculated.

All continuous secondary endpoints will be analysed with continuous estimand 1 (DPS4a).

10.2.2.2 Analytical Approach

The number of participants, mean, median, standard deviation (SD), minimum, and maximum values will be presented at each scheduled visit that the variable is recorded. The following visits should be presented unless otherwise stated: Baseline, 207 week 4, 8, 12, 16 (labelled as "207 / Week X") and 208 week 4, 8, 12, 16, 24, 36 and 40 (labelled as "208 / Week X").

Figures for the mean percentage change and change from baseline in each of the continuous endpoints will be displayed over time. Waterfall plots for the percentage change and change from baseline will also be produced for the same scheduled visits as presented in tables.

10.2.3 Rate Variables Analysis

10.2.3.1 Estimands

The secondary rate endpoints are:

- Number of courses per patient-year of any TCS/TCI rescue medication (excluding antibacterial rescue)
- Number of courses per patient-year of topical corticosteroids of any potency
- Number of courses per patient-year of topical tacrolimus (0.1%), topical pimecrolimus (1%) or grade VII topical corticosteroid
- Number of courses per patient year of moderate potency (grade IV and V) topical steroids

The population summary measure of interest will be the number of events per patient-year.

Intercurrent events for rate endpoints looking at rescue medication will be accounted for in the following manner:

Table 4: Intercurrent Event Strategies for Rate Estimand 1

Discontinuation of treatment	The use of prohibited medications or TCS/TCI rescue therapy, non-compliance with study drug, any deviations from protocol
While on treatment strategy Exclude all data collected more than 30 days after the last dose of IMP	Treatment policy strategy: Data will be used as collected

Data point sets DPS1 and DPS2 will be used for all secondary rate endpoints.

10.2.3.2 Analytical Approach

The rate of each endpoint per patient year will be presented for each treatment group.

In addition the number of patients with 0, 1, 2, 3 or more courses and with at least one course will be displayed.

Histograms for the number of rescue therapy periods, topical corticosteroid periods, topical tacrolimus, pimecrolimus or grade VII corticosteroid periods and moderate potency topical steroids periods will be produced.

The proportion of participants using rescue therapy, topical corticosteroids, topical tacrolimus, pimecrolimus or grade VII corticosteroid and moderate potency topical steroids periods will be also be plotted.

10.3 Exploratory Efficacy Analysis

10.3.1 Time to Event Analysis

10.3.1.1 Estimands

The exploratory time to event endpoints are:

- Time to first achievement of EASI-50
- Time to first achievement of sustained EASI-50 (See section 5.3.3.1)

The population summary measure of interest will be the cumulative percentage of participants achieving response at each scheduled visit.

Intercurrent events for the exploratory time to event endpoints will be accounted for in the following manner:

Table 5: Intercurrent Event Strategies for Time to Event Estimand 1

Use of TCS/TCI rescue medications within 4 weeks or type 1 prohibited meds from 207, use at any time of other prohibited medications for atopic dermatitis	Treatment discontinuation, non-compliance with treatment, other deviations from the protocol
Composite strategy Participants will be considered as ‘non-responders’ 1) within 4 weeks after the use of TCS/TCI rescue medications or type 1 prohibited meds from 207 2) at any time after the use of other prohibited medications for atopic dermatitis	Treatment policy strategy: Data will be used as collected

For all exploratory time to event endpoints data point set DPS4b will be used.

10.3.1.2 Analytical Approach

The number of participants meeting the criteria for the endpoint and the number of participants ‘at risk’ of meeting the criteria at each visit will be presented together with the cumulative incidence. Cumulative incidence is calculated as the total number of events on or before the visit divided by the total number of participants at risk of the event. Unless otherwise stated, the results will be summarised at the following visits: Baseline, 207 week 4, 8, 12, 16 (labelled as “207 / Week X”) and 208 week 4, 8, 12, 16, 24, 36 and 40 (labelled as “208 / Week X”).

Plots for the cumulative incidence of participants achieving EASI-50 and sustained EASI-50 over time will be produced for each treatment group.

10.3.2 Continuous Variables Analysis

10.3.2.1 Estimands

The exploratory continuous endpoints in set 1 are:

- Change and percentage change from baseline in each of the four body-region scores of the EASI
- Daily absolute change from baseline in PP-NRS and SD-NRS scores

The population summary measure of interest will be the mean change from baseline at each scheduled visit for the body-region scores endpoint and daily for PP-NRS and SD-NRS endpoints.

The exploratory continuous endpoints in set 1 will be analysed with continuous estimand 1 (DPS4a). Intercurrent events for the exploratory continuous endpoints in set 1 will be accounted for as described in Table 3 for continuous estimand 1.

The exploratory continuous endpoints in set 2 are:

- Change from baseline in ADCT score

The population summary measure of interest will be the mean change from baseline at each scheduled visit.

Intercurrent events for the exploratory continuous endpoints in set 2 will be accounted for in the following manner:

Table 6: Intercurrent Event Strategies for Continuous Estimand 3

For all possible intercurrent events
Treatment policy strategy:
Data will be used as collected at scheduled visits

The exploratory continuous endpoints in set 2 will use data point set DPS4.

